5.1.3 Statistical Methods for Exploratory Objective(s)

No hypotheses will be tested.

Ratio between binding antibody (ELISA) concentration and neutralizing antibody titer will be calculated and provided with 95% CI by intervention arm and main effects group. Analyses will be conducted on overall population and by age group.

Immunogenicity parameters for antibody persistence will be described with 95% CI for each age and vaccine group. The Reverse Cumulative Distribution Curves and distribution tables will also be produced in each age and vaccine group.

Last available neutralizing antibody titer and binding antibody (ELISA) concentration before infection will be described with 95% CI in aggregated vaccine group and aggregated placebo group.

Cell-Mediated Immunity

All cytokines collected will be summarized by visit.

TH1/TH2 ratios below will be summarized by treatment group on overall population and by age group for data collected at D22 and D36:

1. IFNg/ IL-4
2. IFNg/IL-5
3. IFNg /IL-13
4. IL-2 /IL-4
5. IL-2 /IL-5

6. IL-2/IL-13
7. TNFa/IL-4
8. TNFa/IL-5
9. TNFa/IL-13

The ratios above are based on fold-rise as defined in [Section 4.4.3.1](#). That is for each cytokine, there are two Th1/TH2 ratios, one for each subtraction described in [Section 4.4.3.1](#). The ratio based on subtraction of spike stimulate – negative control will be used as main supportive information for Th1/Th2 results. Among all ratios listed, IFNg/IL-4 is the main TH1/TH2 ratio for characterizing Helper T cell polarization.

Post-vaccination antibody titers for the different study arms may be compared with human convalescent sera antibody titers, conditional to convalescent sample availability.

For descriptive purposes, the statistics presented on [Table 5.1](#) will be produced.

A principle component analysis (PCA) will be performed on collected CMI data to identify linear combinations, i.e., principle components, of the biological variables. PCA analyses will be conducted for the two subtractions described in [Section 4.4.3](#), separately. All cytokines will be involved in the PCA analysis. The variables were \log_{10} -transformed and centered to 0 mean and scaled to the standard deviation; the covariance matrix will be used and for each analysis two principal components (PC1 and PC2) will be extracted accounting for a given proportion of data variability. Each component will be characterized by its loadings, i.e., weights quantifying how much each original variable contributes to the component. PCA will be applied to PPAS-CMI analysis set.

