In addition to antibody response 21 days after the first injection, durability after a single injection also needs to be taken into account for schedule selection decisions, as peak immune responses after 1 injection may be adequate but could (at least theoretically) wane rapidly, potentially leaving vaccinees at risk in the event of ongoing circulation of the novel coronavirus. A further consideration is allowing sufficient time for contraction of innate immune responses and expansion of the adaptive immune response after dosing, which would be underestimated if evaluated too soon after the dose. In this regard, at least fourteen days after a second dose is deemed sufficient, based on experience with other vaccines (27) (31) (32). Therefore, antibody titers at D22 (21 days after the first injection) and D36 (14 days after a second injection) after a single injection or after 2 injections are considered relevant for informing schedule selection.

Rationale for Primary Immunogenicity Endpoint

Human experimental coronavirus infection studies have identified that the presence of pre-challenge neutralizing antibodies were predictive of protection from infection or symptoms following challenge (33) (34). For this reason, neutralizing responses are expected to provide the most relevant functional evaluation of immune responses for this vaccine candidate.

Rationale for Study Population

The study will enroll participants with no history of COVID-19 or serologic evidence of SARS-CoV-2 infection by rapid diagnostic test at the baseline visit. Inclusion of individuals with prior exposure to SARS-CoV-2 would be expected to influence immunogenicity measures. This trial is geared to identifying the dose-level of CoV2 preS dTM vaccine formulation that best supports an immune response in the naïve population, considered the population most at need for a preventive solution against SARS-CoV-2. Therefore, the immunogenicity and safety data in this study are targeted to be generated in individuals without evidence of prior exposure to SARS-CoV-2 infection.

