9.4.4 Exploratory Endpoint

9.4.4.1 Immunogenicity

Th1 and Th2 cytokines will be measured and summarized for individual and aggregate study arms.

Detailed CMI analyses will be defined in the SAP. The CMI analysis will be based on PPAS-CMI set.

The ratio between binding antibody (ELISA) concentration and neutralizing antibody titer will be summarized for individual and aggregate study arms. The ratio (neutralizing antibody / binding

antibody) will be calculated as difference in \log_{10} scale and with the 95% CIs calculated using normal approximation will be provided. The analyses will be performed on PPAS-IAS, unless otherwise specified.

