4.4.3 Cell-Mediated Immunity

4.4.3.1 Cell-Mediated Immunity Assessment Methods

Helper T cell type 1 (TH1) and Helper T cell type 2 (TH2) Cytokines will be collected for CMI analyses. TH1 cytokines include IFN-gamma (IFNg), Interleukin (IL)-2, IL-6, Tumor Necrosis Factor alpha (TNF α). TH2 cytokines include IL-4, IL-5, IL-10, IL-13. Additionally, Helper T cell type 17 (TH17) cytokine IL-17 and Granulocyte-macrophage-colony-stimulating Factor (GM-CSF)-producing T Helper (THGM) will also be collected and measured.

The list of cytokines is subject to be updated based on more information and knowledge on SARS-CoV-2 before the enrollment of participants of Cohort 2.

All cytokines above will be measured in whole blood following stimulation with pools of S-antigen peptides or full length S protein at D0, D22, and D36 for randomly selected participants from each study intervention group in Cohort 2.

Computed values for analysis

For each participant and each cytokine listed above, 3 measurements will be available for analysis. The 3 measurements are positive control, negative control, and spike stimulant. Each measurement has its own LLOQ and upper limit of quantification (ULOQ). Similar as described in [Section 4.4.2.1](#), the computational rule below is applied to the CMI measurements.

- If a value is < LLOQ, then use the computed value LLOQ/2
- If a value is between \geq LLOQ and < ULOQ, then use the value
- If a value is \geq ULOQ, then use the computed value ULOQ

Two subtractions will be calculated as below for each cytokine with computed values described above:

- Subtraction 1: (spike stimulant – negative control)
- Subtraction 2: (positive control - negative control)

Fold-rise

To derive the fold-rise of cytokines, the ratio of post-vaccination and baseline values of the corresponding subtractions above are used. Therefore, there are 2-fold rise ratios for each cytokine per participant per visit with CMI samples:

- Value of a post-baseline visit (spike stimulant – negative control) / baseline value of (spike stimulant – negative control)
- Value of a post-baseline visit (positive control – negative control) / baseline value of (positive control – negative control)

Note: If baseline or post-baseline computed value is missing, then fold-rise is missing.

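### The main Th1/Th2 readout (IFNg/IL-4 on fold-rises) measures change in balance from D01, not the balance after vaccination, and its D01 divisor may be near background with no rule for zero or negative values

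*SAP*

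**What the plan says.** SAP 4.4.3.1 replaces values below LLOQ by half the LLOQ, subtracts the negative control, and defines the main cytokine fold-rise as "Value of a post-baseline visit (spike stimulant – negative control) / baseline value of (spike stimulant – negative control"). The fold-rise is set to missing only when a baseline or post-baseline computed value is missing.

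SAP 5.1.3 states: "TH1/TH2 ratios below will be summarized by treatment group on overall population and by age group for data collected at D22 and D36". On construction it says "The ratios above are based on fold-rise as defined in" SAP 4.4.3.1. On priority it says "The ratio based on subtraction of spike stimulate – negative control will be used as main supportive information for Th1/Th2 results", and "Among all ratios listed, IFNg/IL-4 is the main TH1/TH2 ratio for characterizing Helper T cell polarization". The same section also plans a by-visit summary of every cytokine and a principal component analysis. No hypotheses are tested.

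Protocol 9.4.4.1 says "Th1 and Th2 cytokines will be measured and summarized for individual and aggregate study arms" and leaves CMI detail to the SAP. For its other exploratory ratio, neutralizing over binding antibody, that section works from levels: a difference in log10 with a 95% CI.

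On the population, Protocol 4.2 says "The study will enroll participants with no history of COVID-19 or serologic evidence of SARS-CoV-2 infection". SAP 5.4 includes the CMI analyses, except the principal component analysis, in the first interim analysis, which supports formulation selection.

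**The concern.** Polarization is a property of the response: how much Th1 cytokine there is relative to Th2 cytokine once the participant has been vaccinated. The named readout divides that quantity by the same ratio at D01. A value of 1 means only that both cytokines rose by the same factor, whatever the balance.

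The question matters to this programme. Protocol sections 2 and 4.2 give a balanced Th1/Th2 response as a reason for choosing AS03 and AF03 and as one of several mitigations of the theoretical risk of enhanced disease. Concern about immunopathology with unadjuvanted or Th2-based vaccines is also why older adults are kept out of the unadjuvanted arm. Someone reading the interim tables could take a value above 1 as Th1-dominant and a value below 1 as Th2-dominant. The construction supports neither reading.

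**Working it through.** **Inputs.** The definitions and subset sizes come from SAP 3.1, 4.4.3.1, 5.1.3 and 5.5. The documents give no cytokine values, SDs or correlations, so every such number below is an assumption.

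**Subset size, the one figure stated for this analysis.** Age 18-49: 2 × 18 + 4 × 6 = 60. Age ≥ 50: 2 × 9 + 3 × 3 = 27. Total 87, as stated. Pooled over age, the groups are 27 (each AS03 arm), 9 (each AF03 arm, and placebo) and 6 (unadjuvanted).

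**What the readout is.** With F and L the subtracted IFNg and IL-4 values,

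(F_post / F_D01) ÷ (L_post / L_D01) = (F_post / L_post) ÷ (F_D01 / L_D01).

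**Illustrations (invented values, arbitrary units).**

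| D01 IFNg, IL-4 | Post IFNg, IL-4 | Post ratio | D01 ratio | Planned readout |
|---|---|---|---|---|
| 2, 20 | 200, 400 | 0.5 | 0.1 | 5.0 |
| 20, 2 | 400, 200 | 2.0 | 10 | 0.2 |
| 10, 10 | 400, 100 | 4.0 | 1 | 4.0 |
| 20, 5 | 400, 100 | 4.0 | 4 | 1.0 |
| 50, 5 | 400, 100 | 4.0 | 10 | 0.4 |

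The last three rows share one post-vaccination response and report three different values.

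**Precision.** Let s be the SD of the log10 ratio at one visit, equal at D01 and post, and ρ the correlation between the two. The planned readout has SD s√(2(1 − ρ)). The multiplier is 1.41 at ρ = 0, 1.22 at 0.25, 1.00 at 0.5 and 0.71 at 0.75. The 95% CI of the geometric mean is the estimate multiplied and divided by 10^(t·SD/√n):

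| n | Level ratio, s = 0.3 | Planned, ρ = 0 | Planned, ρ = 0.75 | Level ratio, s = 0.5 | Planned, ρ = 0 | Planned, ρ = 0.75 |
|---|---|---|---|---|---|---|
| 27 | 1.31 | 1.47 | 1.21 | 1.58 | 1.90 | 1.38 |
| 18 | 1.41 | 1.63 | 1.27 | 1.77 | 2.25 | 1.50 |
| 9 | 1.70 | 2.12 | 1.46 | 2.42 | 3.50 | 1.87 |
| 6 | 2.06 | 2.79 | 1.67 | 3.35 | 5.52 | 2.35 |

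At ρ = 0.5 the planned readout and the level ratio have the same width. At n = 3 (older adults outside the AS03 arms) neither is informative: at s = 0.5 the factor is 17 for the level ratio and 57 for the planned readout at ρ = 0.

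**Comparison between arms.** Simulation with 18 per arm, s = 0.4 and a true difference of 0.5 log10 gave a mean difference of 0.50 for both measures. At ρ = 0 the standard errors were 0.188 (planned) and 0.133 (levels). These match 0.4 × √2 × √(2/18) = 0.189 and 0.4 × √(2/18) = 0.133. At ρ = 0.5 they were equal to within simulation error. Within one simulated arm, a true post-vaccination geometric mean ratio of 1.0 was reported as 0.50, because the assumed D01 log10 ratio was 0.3 and 10^−0.3 = 0.50.

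**Whether the divisor is defined.** If spike-stimulated and negative-control values have the same distribution at D01, about half of the subtractions are zero or negative for each cytokine. With independent cytokines, both are positive in 0.5 × 0.5 = 25% of participants: 4.5 of 18, or 1.5 of 6. Positive dependence between the cytokines would raise that share. In simulations with log10 SD 0.3, spike shifts of 0 to 0.3 log10, and 0 to 60% of negative controls below a common LLOQ, the share ran from 10% to 58%. When both values fall below a common LLOQ, the subtraction is LLOQ/2 − LLOQ/2 = 0. SAP 4.4.3.1 has no rule for a zero or negative result, and two negative fold-rises would divide to an apparently valid positive ratio.

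**The case against.** The strongest case for the plan has five parts.

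1. If D01 values lie near a common floor, the D01 ratio is roughly constant. The planned readout is then the post ratio times a constant and ranks participants and arms correctly. This stands, and it rules out a stronger reading that a reader might infer: that the readout cannot tell a strongly Th1 response from a strongly Th2 one. Making the two coincide needs very different D01 balances, which sits badly with a near-background D01. What remains is that the constant is unknown and set by assay limits, so a value in one arm still does not state that arm's balance.

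2. Extra noise is not certain. It arises only if ρ is below 0.5; above that, dividing by D01 helps. A low ρ is plausible with a near-floor baseline but is not documented.

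3. A ratio of concentrations has no natural neutral value, because it depends on the units of two assays. This stands. The level ratio has to be read against placebo and D01, and the post ratios in the illustrations cannot be labelled Th1- or Th2-dominant without that reference.

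4. The by-visit cytokine summaries already allow a rough ratio of geometric means at D22 and D36. That is true, but the ratio would lack its own interval because the within-participant covariance is lost. SAP 5.1.3 also does not say whether those summaries use subtracted values.

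5. A reader might infer that the SAP departs from the protocol. It does not: Protocol 9.4.4.1 hands the CMI detail to the SAP. Nor does formulation selection rest on this ratio; primary neutralization and safety data inform it, and the SAP calls the ratio supportive.

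**Conclusion.** The point holds in limited form. By algebra alone, the readout named for polarization is a change in IFNg/IL-4 balance from D01. No participant-level summary of the post-vaccination balance is planned. What is lost is the balance within an arm; unbiased comparison between randomized arms on the log scale is kept wherever the readout is defined.

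The effect on precision ranges from an SD 41% larger (ρ = 0) to 29% smaller (ρ = 0.75) than that of a level ratio, under equal SDs at the two visits. The share of participants with a usable divisor, 10% to 58% in the scenarios tried, rests wholly on assumed distributions. The missing rule for non-positive subtractions does not depend on those assumptions. Because the analysis is exploratory and supportive, this is a low-cost improvement to interpretation.

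**What to change.** In SAP 5.1.3, make the main Th1/Th2 summary the participant-level difference log10 IFNg − log10 IL-4, from background-subtracted spike-stimulated values at D22 and D36. Report it as a geometric mean ratio with 95% CI, and show the D01 and placebo values in the same table. This follows the approach that Protocol 9.4.4.1 takes for the neutralizing/binding ratio. Keep the ratio of fold-rises as a supportive summary.

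In SAP 4.4.3.1, state a floor rule for zero or negative subtractions at any visit, and report how many participants it affects. The level ratio needs this rule too, though for two subtractions per participant and not four.

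Protocol 9.5 and SAP 5.4 record that a partial database lock has taken place. If the cytokine data have already been seen, label the new summary post hoc.

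The cost is SAP wording and one derived variable from data already collected. The downside is a ratio that depends on assay units and must be read against placebo and D01.

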5.2 Analysis Sets

Five main analysis sets will be used: The Per-Protocol Analysis Set (PPAS), the Per-Protocol Analysis Set for immunogenicity (PPAS-IAS), the Per-Protocol Analysis Set for CMI (PPAS-CMI), the Full Analysis Set (FAS), and the Safety Analysis Set (SafAS).

5.2.1 Full Analysis Set

Subset of randomized participants who received at least 1 injection of the study intervention. Subjects will be analysed according to the vaccine group to which they were randomized.

5.2.2 Safety Analysis Set

Subset of randomized participants who have received at least one injection of study intervention. Participants will have their safety analyzed according to the study intervention they actually received. All subjects will be analyzed after each dose according to the vaccine they actually received, and after any dose according to the vaccine received at the 1st dose.

Safety data recorded for a vaccine received out of the protocol design will be excluded from the analysis (and listed separately).

5.2.3 Per-Protocol Analysis Set

Subset of the FAS. Participants presenting with at least one of the following conditions will be excluded from the PPAS:

- Participant did not meet all protocol-specified inclusion criteria or met at least one of the protocol-specified exclusion criteria
- Participant did not complete the protocol-defined vaccination schedule
- Participant received a study intervention other than the one that he / she was randomized to receive
- Preparation and / or administration of study intervention was not done as per-protocol
- Participant did not receive study intervention in the proper time window as defined in the protocol visits.
- Participant received a Category 2 or Category 3 therapy /medication / as stated in Section 6.5 of the Protocol
- Participant with positive test results in the neutralization test at baseline.

The above conditions leading to exclusion from the PPAS may be detailed and completed if necessary following the data review. In any case, if PPAS definition is modified, the PPAS definition will be finalized before the database lock and documented in an SAP update.

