7.1.2 Definitive Contraindications

Participants will permanently discontinue (definitive discontinuation) study intervention for the reasons listed below. These participants must not receive any additional dose of study intervention but should continue to be followed for safety. Additional unscheduled visits may be performed for safety reasons and information will be reported in the source documents.

Should a participant experience 1 of the conditions listed below, the Investigator will discontinue vaccination:

- DCI01: Pregnancy, as indicated by a positive urine test
- DCI02: An anaphylactic or other significant allergic reaction to the previous dose of vaccine
- DCI03: SAE assessed as related to the study vaccine following the previous dose of vaccine, based on Investigator's judgment
- DCI04: Grade 3 AE, assessed as related to the study vaccine that, in the opinion of the investigator, may place the participant at unreasonable or significant risk of injury or illness following repeat exposure to study vaccine

In the event of a local or national immunization program with a SARS-CoV-2 or a COVID-19 pandemic vaccine, participants who receive SARS-CoV-2 or a COVID-19 pandemic vaccine at any time during the study will not be withdrawn from the study. As efficacy has not been demonstrated for any of the investigational formulations under evaluation in the current study, it is not required to unblind participants to the VAT00001 study assignment prior to administration of an authorized COVID-19 vaccine.

If the participant receives an authorized approved COVID-19 vaccine, this information would be collected and the participant's data up to the point of receipt of authorized/approved vaccine will be included in the primary analysis for immunogenicity and safety. Participants will continue to be followed for the duration of the study as per scheduled visits and procedures.

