9.3 Populations for Analyses

The following populations are defined:

Population	Description
Randomized	All participants with a randomized group that has been allocated by IRT
Safety Analysis Set (SafAS)	Subset of randomized participants who have received at least one injection of study intervention. Participants will have their safety analyzed according to the study intervention they actually received. Safety data recorded for a vaccine received out of the protocol design will be excluded from the analysis (and listed separately).
Full analysis set (FAS)	Subset of randomized participants who received at least 1 injection of the study intervention. Participants will be analyzed according to the study intervention group to which they were randomized.
Per-protocol analysis set (PPAS)	Subset of the FAS. Participants presenting with at least one of the following relevant conditions will be excluded from the PPAS: 
 • Participant did not meet all protocol-specified inclusion criteria or met at least one of the protocol-specified exclusion criteria • Participant did not complete the protocol-defined vaccination schedule • Participant received a study intervention other than the one that he / she was randomized to receive • Preparation and / or administration of study intervention was not done as per-protocol • Participant did not receive study intervention in the proper time window • Participant received a Category 2 or Category 3 therapy / medication / as stated in Section 6.5 • Participant with positive test results in the ELISA and/or neutralization test at baseline • Additional conditions for exclusion may be identified during the review of protocol deviations; such conditions will be documented in the Statistical Analysis Plan (SAP)
Per-protocol analysis set for immunogenicity (PPAS-IAS)	Subset of PPAS excluding participants who provided all post-dose serology samples outside the proper time window or no post-dose serology sample was drawn.
Per-protocol analysis set for CMI (PPAS-CMI)	Subset of PPAS excluding participants who provided all post-dose CMI samples outside the proper time window or no post-dose CMI sample was drawn.

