‡ Safety laboratory assessments will include: Serum Chemistries (liver enzymes / Chem 7, lipase, and amylase); hematology (complete blood count with differential); Urinalysis; Microscopy. In cases of abnormal safety laboratory results, unscheduled visits may occur, based on Investigator's judgment.

§ BL0001, MC0001, WB0001 and the first safety laboratory assessment sample will be collected at pre-VAC1 (baseline); and BL0002, MC0002, and WB0002 samples will be collected at pre-VAC2.

** Participants will use this DC1 to record information about solicited reactions, unsolicited AEs, SAEs, and AESIs from D01 to D08 after vaccination and will continue to record information about unsolicited AEs, SAEs, and AESIs from D09 to V02.

†† The Investigator or an authorized designee will remind the participants to bring back the DC at the next visit and will answer any questions.

‡‡ The Investigator or an authorized designee will interview the participants to collect the information recorded in the DC and will attempt to clarify anything that is incomplete or unclear.

§§ Participants will use this DC2 to record solicited reactions, unsolicited AEs, SAEs, and AESIs (from V02 to V03) and will continue to collect unsolicited AEs, SAEs, and AESIs (from V03 to V04).

*** Participants will use this DC3 for unsolicited AEs follow-up until D43 and SAEs, AESIs, and COVID-19-like illness follow-up from V04 to V05.

††† Participants will use this DC4 for SAEs, AESIs, and COVID-19-like illness follow-up from V05 to V06.

‡‡‡ Participants will use this DC5 for SAEs, AESIs, and COVID-19-like illness follow-up from V06 to V07.

§§§ During the D09 telephone call, staff will review the DC1 for solicited reactions from D01 to D08 after vaccination, inquire whether the participant experiences any SAE or AESI not yet reported, and remind the participant to bring back DC1 for V02. This telephone call will NOT be documented in the CRF.

**** Prior to these specified time-points, active surveillance will still occur during the established contacts (phone calls and visits).

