5.2.3.1 Per-Protocol Analysis Set for immunogenicity (PPAS-IAS)

Subset of PPAS excluding participants who provided all post-dose serology samples outside the proper time window or no post-dose serology sample was drawn

For participants with just part of expected post-dose serology samples outside the proper time window or without a valid test result, participants will be kept in PPAS-IAS and only samples within the time window and with a valid result will be included in immunogenicity analyses.

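### A single participant-level per-protocol set removes valid Cohort 2 D22 samples, drawn before the second injection, for events that occur only after the draw

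*SAP*

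**What the plan says.** SAP 5.2.3 takes one PPAS from the FAS by excluding participants, not samples. Its conditions include "Participant did not complete the protocol-defined vaccination schedule" and, for timing, "Participant did not receive study intervention in the proper time window as defined in the protocol visits". Faulty handling also counts ("Preparation and / or administration of study intervention was not done as per-protocol"), and so does interfering medication ("Participant received a Category 2 or Category 3 therapy /medication / as stated in Section 6.5 of the Protocol"). Receiving an intervention other than the randomized one also excludes. No condition is tied to a visit or to the sample it could affect. Protocol 9.3 carries nearly the same list (for timing, "Participant did not receive study intervention in the proper time window"). It describes the conditions as relevant ones but gives no rule by time point.

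PPAS-IAS and PPAS-CMI are subsets of the PPAS (SAP 5.2.3.1 and 5.2.3.2). The one sample-level rule, in 5.2.3.1, is for participants who are already in the PPAS: "only samples within the time window and with a valid result will be included in immunogenicity analyses".

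Neutralizing titer at D22 is a primary endpoint in every group (SAP 2.1 and 5.1.1.4). For Cohort 2, a footnote to SAP Table 3.2 states that "BL0002, MC0002, and WB0002 samples will be collected at pre-VAC2". SAP 5.2.5 places the main serology analyses on the PPAS-IAS and the CMI analyses on the PPAS-CMI, and confirms both on the FAS.

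The contraindications to further injection apply to Cohort 2 only (Protocol 7.1). One of them, in 7.1.2, turns on the hazard of a repeat dose and begins: "Grade 3 AE, assessed as related to the study vaccine that, in the opinion of the investigator, may place the participant at unreasonable or significant". Participants stopped under 7.1.2 stay in safety follow-up.

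**The concern.** A sample drawn before the second injection cannot be altered by what happens at that injection or later. Excluding it for such an event conditions a D22 result on the future and discards a valid measurement.

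The exclusion is also one-sided. At the D22 draw both cohorts have had one injection. Cohort 1 completed its schedule on D01, whereas Cohort 2 is filtered again on a second injection still to come. Some grounds for withholding that injection (allergic reaction, related SAE, related Grade 3 AE) are consequences of the first, so removal need not be independent of the response to it.

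What is at stake is the main D22 description in Cohort 2 and its comparability with Cohort 1. SAP 5.1.1.4 summarizes the primary endpoints by injection schedule, and Protocol 4.2 treats D22 and D36 titers as relevant to schedule selection.

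**Working it through.** **1. The plan's own numbers.** From Protocol Table 4.2:
- Two-injection adjuvanted arms: (20+60+20+60) + (10+30+10+30) = 240. One-injection adjuvanted arms: 4×20 + 4×10 = 120. Both match Protocol 9.2 and SAP 5.1.1.4.
- All of Cohort 2, with the unadjuvanted and placebo arms: 200 + 90 = 290.
- The smallest Cohort 2 serology arms have 10 participants (older adults, AF03 arms and placebo). In the CMI subset the same older arms have 3 each, and the younger non-AS03 arms have 6 each.

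**2. Which cases lose a valid D22 sample.** The V02 window is D22 to D29.

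| Case in Cohort 2 | Valid in-window D22 sample? | Lost because of the PPAS rule? |
|---|---|---|
| Never attends V02 | No | No |
| V02 itself after D29, draw and injection both late | No; the sample rule in SAP 5.2.3.1 drops it anyway | No |
| V02 in window, second injection withheld | Yes, if drawn | Yes |
| V02 in window, second injection wrong or mis-prepared | Yes | Yes |
| Draw in window, injection after D29 | Yes | Yes, but Protocol 7.1.1 keeps postponement inside the window, so this should be rare |
| Category 2 or 3 medication first taken after the draw | Yes | Yes |

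The medication condition applies to Cohort 1 as well. However, Protocol 6.5 collects reportable medication through the follow-up after each injection. That is to about D22 in Cohort 1 and about D43 in Cohort 2, so Cohort 2 has longer to meet it after the draw.

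**3. Authorized COVID-19 vaccine.** Protocol 6.5 lists other vaccines under Category 2. Read literally, a later authorized vaccine removes the participant, D22 sample included. Taking one instead of the second injection also leaves the schedule incomplete. Yet Protocol 7.1.2 and SAP 5.1 and 5.7 keep data collected before that vaccine in the primary analysis. These passages must be reconciled.

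**4. Number removed.** The documents give no rate. Assume that 3% to 8% of Cohort 2 meet one of the later conditions: 0.03 × 290 = 8.7 and 0.08 × 290 = 23.2, or about 9 to 23. At that rate this is an upper bound, because the first two rows of the table lose nothing valid. It leaves out authorized vaccination months later, for which step 3 notes the contrary rule.

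**5. Precision.** SAP 5 uses a t-based 95% CI on log10 titer, with half-width t(n−1) × SD / √n. At equal SD the ratio of half-widths does not depend on the SD.
- Serology arm, 10 to 9: 2.262/√10 = 0.715; 2.306/√9 = 0.769; 7.5% wider. From 10 to 8: 17% wider.
- Serology arm, 60 to 57: about 3% wider.
- CMI arm, 3 to 2: 4.303/√3 = 2.48; 12.706/√2 = 8.98; about 3.6 times as wide. From 6 to 5: about 18% wider.

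**6. Possible shift in the D22 GMT.** Let f be the share removed and d the mean log10 titer of those removed minus that of those retained. Then retained GMT / GMT of all sampled = 10^(−f×d). With d = ±0.3 (assumed, sign unknown), the ratio is 0.97 or 1.04 at f = 5%, and 0.93 or 1.07 at f = 10%. If removal is unrelated to titer, d = 0 and only the loss of precision remains.

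**The case against.** The strongest reply is that the samples are not lost to the study. SAP 5.2.5 repeats these analyses on the FAS, which keeps everyone with at least one injection. That stands and limits the seriousness. It does not repair the main analysis: the FAS also restores ineligible and baseline-positive participants, so a difference between the two sets cannot be traced to this rule.

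Second, the study is descriptive, and the SAP regression with a schedule term pairs D22 in Cohort 1 with D36 in Cohort 2. A reader might infer that Cohort 2 D22 titers drive the choice of schedule through that model; they do not enter it. They do enter the D22 summaries by arm and by schedule.

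Third, a reader might infer that Cohort 2 is stripped of its more reactogenic participants and that D22 is biased in a known direction. The documents do not support this. They give no frequency for the contraindications and no link between reactogenicity and titer. Nor do they say that the D22 blood is drawn once the second injection is ruled out. Unequal selection is established; its effect is not.

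Fourth, one set for all visits describes D22 and D36 in largely the same people, and the SAP allows the PPAS to be refined before lock. Both are true, but no refinement by visit is written. A partial database lock has already taken place (Protocol 9.5, SAP 5.4) and the first interim unblinds the sponsor at group level, so a change now needs its timing on record.

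**Conclusion.** The point holds, with modest consequences. As written, a Cohort 2 participant with a valid pre-injection D22 sample leaves the primary D22 serology result, and the exploratory D22 CMI result, for something that happens only after the draw. Cohort 1 has no exclusion tied to a second injection, so the D22 sets are selected differently.

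The size rests on an assumed rate: at 3% to 8% of 290, at most 9 to 23 samples. It would be wrong to read that range as the expected loss of valid samples, since missed and late V02 visits lose nothing valid. For a single exclusion, the smallest serology arms lose 1 of 10 (CI 7.5% wider at equal SD) and the smallest CMI arms lose 1 of 3. Whether the D22 GMT shifts, and in which direction, cannot be determined from the documents.

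**What to change.** In SAP 5.2.3 to 5.2.3.2, define per-protocol status by visit:
- A D22 sample is excluded only for conditions arising up to the D22 draw, which in Cohort 2 precedes the second injection. This should cover every dated condition, including Category 2 or 3 medication, and not only the second-injection ones.
- Samples from D36 onward use the full list.
- State how the Category 2 condition fits with the rule that keeps data collected before an authorized COVID-19 vaccine.
- Report the per-protocol N by visit and arm.
- Record the change as an SAP update, with its date relative to the partial lock and the group-level unblinding. If D22 results on the present definition have already been reported, show both.

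The cost is a few lines of SAP text, a visit-level flag in the analysis dataset, and a rerun of the D22 outputs where these already exist. The downside is that the D22 and D36 per-protocol sets will differ slightly, so a reader comparing the two visits needs both Ns.
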